### 4.7 Efficacy Analysis

The facial area inflammatory and non-inflammatory lesion counts will be summarized at each evaluation from Baseline through Week 40/ET. Absolute and percent change in inflammatory and non-inflammatory lesion counts will be summarized at Weeks 4, 12, 24, 36 and 40/ET. The absolute and percent change in inflammatory non-inflammatory lesion counts will also be summarized by prior treatment (SB204 experienced, SB204 naïve).

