3.2 STRUCTURE

This is a multi-center, open label study. Eligible subjects will have completed either NI-AC301 or NI-AC302, regardless of which treatment arm they were assigned to receive in the original study.

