3.6 STUDY POPULATION

Approximately 600 healthy male and female subjects with acne vulgaris on the face, chest, shoulders or back will be allowed to participate in the study if they have successfully completed 12 weeks in either NI-AC301 or NI-AC302.

A subject whose facial acne cleared during NI-AC301 or NI-AC302 is eligible to enroll if all other inclusion criteria and none of the exclusion criteria are met. If a subject enters the pivotal study at age 40 and is 41 at the time they complete participation in the pivotal study, they are eligible for the long term safety study as long as they meet all other study inclusion criteria and none of the exclusion criteria.

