3.7.2 INCLUSION CRITERIA

Each subject must fulfill all of the following inclusion criteria to participate in the study:

- 1. Have a signed written informed consent form. Subjects less than 18 years of age or the age of majority in their state must sign an assent form for the study and a parent or a legal guardian must sign the informed consent;
- 2. Have completed the full 12 weeks of treatment in NI-AC301 or NI-AC302;
- 3. Be in good general health;
- 4. Have no more than two nodules or cysts on the face;
- 5. Women of childbearing potential (WOCBP) must have a negative urine pregnancy test (UPT) prior to enrollment;
- 6. WOCBP must agree to use an effective method of birth control during the course of the study and for 30 days after their final study visit;
- 7. Be willing and able to follow study instructions and likely to complete all study requirements. Subjects under 18 years of age or age of majority must be accompanied by the parent or legal guardian at the time of assent/consent signing.

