4.4 EFFICACY ASSESSMENTS

The same evaluator should perform lesion counting at Weeks 4, 12, 24, 36, and 40/ET. This should be the same evaluator that performed the Week 12 assessments for the NI-AC301 or NI-AC302 study. In the event that this is not possible due to unforeseen circumstances, a different evaluator may evaluate the subject. However, the same evaluator should evaluate subjects at the Baseline and Week 40/ET evaluations. The subject's Week 12 lesion counts from NI-AC301 or NI-AC302 will be considered the Baseline value for this study.

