### 2.4 Efficacy Endpoints

Efficacy endpoints will include absolute and percent change in inflammatory and non-inflammatory facial area lesion counts from baseline at each study visit.

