Figure 14.2.2 Average Percent Change from Baseline in Inflammatory Lesion Count (Face only) Over Time
Safety Population

Figure 14.2.2

Average Percent Change from Baseline in Inflammatory Lesion Count Over Time
Safety Population

Using shell for Figure 14.2.1, repeat for the following:

Figure 14.3.1 Average Change from Baseline in Non-Inflammatory Lesion Count (Face only) Over Time, Safety Population

Using shell for Figure 14.2.2 repeat for the following:

Figure 14.3.2 Average Percent Change from Baseline in Non-Inflammatory Lesion Count (Face only) Over Time, Safety Population

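### Mean percent change in lesion counts is undefined or unstable for subjects who enter clear or nearly clear, yet it is the percent-change statistic the SAP figures plot

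*SAP*

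**What the plan says.** Protocol 4.4 fixes the reference point: "The subject's Week 12 lesion counts from NI-AC301 or NI-AC302 will be considered the Baseline value for this study". That count follows the pivotal treatment period, because inclusion criterion 2 (Protocol 3.7.2) requires subjects to "Have completed the full 12 weeks of treatment in NI-AC301 or NI-AC302". Subjects come from either pivotal arm (Protocol 3.2): "regardless of which treatment arm they were assigned to receive in the original study".

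Protocol 3.6 adds: "A subject whose facial acne cleared during NI-AC301 or NI-AC302 is eligible to enroll", provided the other criteria are met. The inclusion criteria cap nodules and cysts but set no minimum lesion count.

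SAP 2.4 makes the efficacy endpoints "absolute and percent change in inflammatory and non-inflammatory facial area lesion counts from baseline at each study visit". SAP 4.7 summarizes the counts at each visit and adds: "Absolute and percent change in inflammatory and non-inflammatory lesion counts will be summarized at Weeks 4, 12, 24, 36 and 40/ET". It repeats the two changes by prior treatment (SB204 Experienced, SB204 Naïve). Table shells 14.2.2.x and 14.2.3.x give N, mean, SD, median and range for all three quantities. The mock figures include Figure 14.2.2, "Average Percent Change from Baseline in Inflammatory Lesion Count Over Time", and Figure 14.3.2 for non-inflammatory lesions.

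SAP 4.1 and 4.7, the shells and Listing 16.2.7.1.1 give no rule for a Baseline of 0. No planned display refers to the count before pivotal treatment.

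**The concern.** Percent change divides by the Baseline count. Here that count is taken after 12 weeks of SB204 or vehicle, and the design expressly allows it to be 0. Two things follow.

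- **Undefined values.** A subject with a Baseline of 0 has no percent change, whether the face stays clear or three lesions appear. Following the plan as written, these subjects leave the percent-change columns. The loss is selective, because they cannot improve.
- **Small denominators.** A subject going from 1 to 5 lesions contributes +400%, and one going from 2 to 8 contributes +300%, for absolute rises of 4 and 6. A few such subjects can set the mean.

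The two effects pull in opposite directions. Their net result depends on how many subjects enter clear or nearly clear, which says little about what SB204 does during the extension. At stake is whether the plotted percent-change curves show the right size, or even the right sign. Separately, no planned display shows how large a retained benefit is relative to the pre-treatment count.

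**Working it through.** The plan gives no figure to reproduce. Efficacy is descriptive, and Protocol 7.9 and SAP 3.6 state that no power calculation was done. All lesion counts below are assumptions; only the approximate N of 600 comes from the documents.

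**Step 1. Formula.** Percent change = 100 × (visit count − Baseline) / Baseline.

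- 0 to 0 and 0 to 3: undefined (division by zero).
- 1 to 5: 100 × 4/1 = +400%. 2 to 8: 100 × 6/2 = +300%.
- 20 to 14: 100 × (−6)/20 = −30%.

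**Step 2. Subjects lost.** If 1%, 5% or 10% of 600 subjects have a Baseline of 0, the percent-change N falls to 594, 570 or 540.

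**Step 3. Effect of a few small Baselines.** Let a share s go from 1 to 5 and the rest from 20 to 14.

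- Mean percent change = 400s − 30(1 − s).
- Mean absolute change = 4s − 6(1 − s).
- Percent change in mean count = 100 × {[5s + 14(1 − s)] / [s + 20(1 − s)] − 1}.

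| s | Mean % change | Median % change | Mean absolute change | % change in mean count |
|---|---|---|---|---|
| 1% | −25.7 | −30 | −5.9 | −29.8 |
| 2% | −21.4 | −30 | −5.8 | −29.6 |
| 5% | −8.5 | −30 | −5.5 | −28.9 |
| 10% | +13.0 | −30 | −5.0 | −27.6 |

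The mean changes sign at s = 30/430 = 7.0%. The other three statistics barely move.

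**Step 4. A full distribution of Baselines.** Assume each subject's underlying count is gamma-distributed (overall mean m = 8, 12 or 16; shape k = 0.8, 1.2 or 2). Baseline and follow-up are independent Poisson counts around it, with follow-up multiplied by 1.0 (no true change) or 0.85 (true 15% fall). There are nine scenarios for each multiplier, with 400,000 simulated subjects in each; percent change is taken where Baseline exceeds 0.

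The share with a Baseline of 0 is [k/(k + m)]^k. It runs from (2/18)² = 1.2% to (0.8/8.8)^0.8 = 14.7%.

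| | No true change | True 15% fall |
|---|---|---|
| Mean % change | about +10% to +17% | about 0% to −6.5% |
| Median % change | 0% | about −15% to −18% |
| Mean absolute change | about 0 | about −15% of the Baseline mean |

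Repeat runs differ by a few tenths of a percentage point. The small-denominator effect outweighs the selective loss of zero Baselines in every scenario, so the mean is shifted towards worsening.

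**Step 5. Retained benefit.** A subject with 25 lesions before the pivotal study, 10 at its Week 12 and 10 at Week 40 of this study shows 100 × (10 − 10)/10 = 0% from the planned Baseline. From the pre-treatment count the figure is 100 × (10 − 25)/25 = −60%.

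**The case against.** The strongest reply is that the plan already contains the correctives. The shells print counts, absolute change and the median beside the mean. A smaller N in the percent-change column reveals the missing subjects, who stay in the count and absolute-change columns. Listing 16.2.7.1.1 shows every value. Efficacy is descriptive in an open-label, single-arm safety study, and the lesion counts used above are assumed. All of this stands, and it limits the point to one statistic. It does not rescue that statistic: the figure titles select the average for plotting, and even the median percent change omits zero-Baseline subjects.

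Three stronger readings are tempting, and the documents do not support them.

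- A reader might infer that the Week 12 Baseline is itself a mistake. It is stated consistently in both documents and isolates change during the open-label period. Replacing it with the pre-treatment count would change the estimand, mix in the blinded period and, for Naïve subjects, include 12 weeks of vehicle.
- A reader might infer that the plan cannot show whether benefit is maintained. For Experienced subjects, change from the end of the pivotal study addresses exactly that: near zero means held, a rise means lost. Only the size relative to pre-treatment is missing. For Naïve subjects the Baseline was taken on vehicle, so there is no earlier SB204 benefit to maintain.
- A reader might infer that the figures lack a split by prior treatment. The titles name none, but the figure bodies are not reproduced in the available text, so this cannot be established.

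**Conclusion.** The point holds for mean percent change only. The design admits zero and near-zero Baselines, the SAP has no rule for them, and the statistic chosen for Figures 14.2.2 and 14.3.2 is the one they distort. Under the assumed gamma-Poisson counts the mean is about 10 to 17 percentage points too high with no true change, and it hides most or all of a true 15% fall. In the two-group illustration the sign reverses once about 7% of subjects go from 1 to 5 lesions. The real size is unknown, because the documents give neither a count distribution nor the share of subjects entering clear.

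The planned counts, absolute changes and medians by visit and prior treatment are sound, apart from the median percent change omitting zero Baselines. No safety, tolerability or exposure output is affected, so the primary objective stands. The change is worth making because a reader of the percent-change figures could be misled in size or direction, and correcting it needs analysis work only.

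**What to change.** Keep the Week 12 Baseline and the absolute-change summaries. Then:

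1. In Figures 14.2.2 and 14.3.2, replace the average with the median percent change, or with the percent change in mean count, which keeps zero-Baseline subjects. Make the chosen statistic the headline percent-change result in Tables 14.2.2.x and 14.2.3.x.
2. State in SAP 4.7 that percent change is not calculated at a Baseline of 0. Report the number of such subjects for each lesion type, and their counts at each visit.
3. As a supplement and not a replacement, add percent change from the pre-treatment pivotal count, shown separately for SB204 Experienced and SB204 Naïve, so that the size of benefit retained by Experienced subjects is visible.

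The cost is SAP and shell wording plus a merge of one variable per lesion type. The analysis already draws on the pivotal data for treatment arm, first-dose date and Week 12 counts. Visits, assessments and treatment are unchanged. The downsides are two reference points to explain, and an assumption, not stated in these documents, that pivotal entry counts were above 0.

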#### 4.8 Deviations from SAP

Any deviations from the original statistical plan will be described and justified in the final clinical study report.

Protocol: NI-AC303

A Phase 3 Multi-Center, Open Label Study Evaluating the Long Term Safety of SB204 Once Daily in the Treatment of Acne Vulgaris.

Mock Data Displays- Tables Version 1.0 Date: 12Apr2017

Prepared for:
Novan Inc.
[name]

Prepared by:
Chiltern International
[name]

This document is the confidential information of Novan Inc. It may not be disclosed to parties not associated with the clinical investigation or used for any purpose without the prior written consent of Novan Inc.

Table 14.3.3.10.2 Treatment Emergent Adverse Events Leading to Death by Extent of Exposure Safety Population	22
Table 14.3.3.11.1 Treatment-Related Treatment Emergent Adverse Events Leading to Death by Duration of Exposure Safety Population	22
Table 14.3.3.11.2 Treatment-Related Treatment Emergent Adverse Events Leading to Death by Extent of Exposure Safety Population	22
Table 14.3.3.13 Summary of Treatment Emergent Adverse Events (TEAE) by Highest Severity, System Organ Class and Preferred Term Safety Populat	tion23
Table 14.3.3.14 Summary of Treatment-Related Emergent Adverse Events (TEAE) by Severity, System Organ Class and Preferred Term Safety Population	ion24
Table 14.3.4 Summary of Vital Signs Safety Population	25

Protocol Number: NI-AC303

Table 14.1.1.1
Subject Disposition
Safety Population

	SB204
	(N=XXX)
SAF Population	xx (xx.x)
Treatment-naïve at enrollment	xx (xx.x)
Previously on SB204 at enrollment	xx (xx.x)
Completed Study	xx (xx.x)
SB204 Experienced	xx (xx.x)
SB204 Naïve	xx (xx.x)
Discontinued Early	xx (xx.x)
Primary Reason for Study Discontinuation [a]	
Adverse Events	xx (xx.x)
Lack of Efficacy as Determined by Investigator	xx (xx.x)
Withdrawal by Subject	xx (xx.x)
Physician Decision	xx (xx.x)
Protocol Violation	xx (xx.x)
Lost to Follow-up	xx (xx.x)
Pregnancy	xx (xx.x)
Worsening of Condition	xx (xx.x)
Other	xx (xx.x)

Notes: Safety (SAF) Population includes all subjects that have been dispensed study drug and received at least one dose of SB204.

Unless stated otherwise, denominator is the number of subjects in safety population.

[a] Denominator is the number of subjects who were randomized.

Source: Listing xx.x.x.x, Program: xxxxx.sas, Output: T xx.x x x xxxx.rtf, Generated on: DDMMMYYYY HH:MM

Page x of y Novan Inc. Protocol Number: NI-AC303

Table 14.1.1.2 Summary of Protocol Deviations Safety Population

Protocol Deviations	SB204 (N=XXX)
Subjects with Any Protocol Deviation	xxx (xx.x)
Deviation A	xxx (xx.x)
 Deviation B	xxx (xx.x)
 Deviation C	xxx (xx.x)
Etc.	

Note (s): Percentages are based on the number of subjects in safety population. Reference: Listing 16.2.x

Protocol Number: NI-AC303

Table 14.1.2.1
Demographics
Safety Population

	SB204 Experienced	SB204 Naïve	Overall
	(N=XXX)	(N=XXX)	(N=XXX)
Age (years)			
n	XXX	xxx	XXX
Mean (SD)	xx.x (xx.xx)	xx.x (xx.xx)	xx.x (xx.xx)
Median	XX.X	XX.X	XX.X
Min, Max	X.X, XX.X	x.x, xx.x	x.x, xx.x
Age Group			
Juvenile (Age <18 years)	xx (xx.x)	xx (xx.x)	xx (xx.x)
Adult (Age 18+ years)	xx (xx.x)	xx (xx.x)	xx (xx.x)
Race			
White	xx (xx.x)	xx (xx.x)	xx (xx.x)
Black or African American	xx (xx.x)	xx (xx.x)	xx (xx.x)
American Indian or Alaska Native	xx (xx.x)	xx (xx.x)	xx (xx.x)
Native Hawaiian or Other Pacific			
Islander	xx (xx.x)	xx (xx.x)	xx (xx.x)
Asian	xx (xx.x)	xx (xx.x)	xx (xx.x)
Other	xx (xx.x)	xx (xx.x)	xx (xx.x)
Ethnicity			
Hispanic or Latino	xx (xx.x)	xx (xx.x)	xx (xx.x)
Not Hispanic or Latino	xx (xx.x)	xx (xx.x)	xx (xx.x)
Sex			
Male	xx (xx.x)	xx (xx.x)	xx (xx.x)
Female	xx (xx.x)	xx (xx.x)	xx (xx.x)
Previously in Study			
NI-AC301	xx (xx.x)	xx (xx.x)	xx (xx.x)
NI-AC302	xx (xx.x)	xx (xx.x)	xx (xx.x)

Note(s): Percentages are based on the number of subjects in safety population. Age is based on the date of informed consent from the previous study (NI-AC301 or NI-AC302); LTS = Long Term Safety Study.

Source: Listing xx.x.x.x, Program: xxxxx.sas, Output: T\_xx.x\_x\_x\_xxxx.rtf, Generated on: DDMMMYYYY HH:MM

Novan Inc. Page x of y Protocol Number: NI-AC303

Table 14.1.2.2
Child Bearing Potential and Contraceptive Use (Females Only)
Safety Population

	SB204
	(N=XXX)
If Female, of Childbearing Potential?	
Yes	xx (xx.x)
No	xx (xx.x)
If No to Childbearing Potential, Why	
Post-Menopausal	xx (xx.x)
Hysterectomy or Bilateral Oophorectomy	xx (xx.x)
Surgically Sterilized	xx (xx.x)
If Yes to Childbearing Potential, Primary Method of Birth Cont	rol
Oral Contraceptive	xx (xx.x)
Intra-Uterine Device	xx (xx.x)
Condom with Spermicide	xx (xx.x)
Diaphragm with Spermicide	xx (xx.x)
Implant	xx (xx.x)
Nuvaring	xx (xx.x)
Medroxyprogesterone Injection	xx (xx.x)
Transdermal Patch	xx (xx.x)
Abstinence	xx (xx.x)
Other	xx (xx.x)

Note(s): Percentages are based on the number of female subjects in Safety population. Source: Listing xx.x.x.x, Program: xxxxx.sas, Output: T xx.x x x xxxx.rtf, Generated on: DDMMMYYYY HH:MM Novan Inc. Page x of y Protocol Number: NI-AC303

Table 14.1.3

Medical History by System Organ Class and Preferred Term
Safety Population

Body System Class	SB204
Preferred Term	(N=XXX)
Subject with Any Medical History	xx (xx.x)
System Organ Class 1	xx (xx.x)
Preferred Term 1	xx (xx.x)
Preferred Term 2	xx (xx.x)
 Preferred Term n	xx (xx.x)
System Organ Class n	xx (xx.x)
Preferred Term 1	xx (xx.x)
Preferred Term 2	xx (xx.x)
 Preferred Term n	xx (xx.x)
	/
Sustan Organ Class a	xx (xx.x)
System Organ Class q Preferred Term 1	xx (xx.x)
Preferred Term 2	xx (xx.x)
Preferred Term 2	xx (xx.x)

Note(s): All investigator terms were coded using MedDRA dictionary version 18.1.

Source: Listing xx.x.x.x, Program: xxxxx.sas, Output: T\_xx.x\_x\_x\_xxxx.rtf, Generated on: DDMMMYYYY HH:MM

Protocol Number: NI-AC303

Table 14.1.4

Adverse Events Ongoing at the Start of the Study by System Organ Class, Preferred Term, and Extent of Exposure Safety Population

System Organ Class Preferred Term	SB204 Experienced (N=XXX)	SB204 Naïve (N=XXX)	Overall (N=XXX)
Number of Subjects with at Least One Event	xx (xx.x)	xx (xx.x)	xx (xx.x)
Number of Events	XX	XX	xx
System Organ Class 1	xx (xx.x)	xx (xx.x)	xx (xx.x)
Preferred Term 1	xx (xx.x)	xx (xx.x)	xx (xx.x)
Preferred Term 2	xx (xx.x)	xx (xx.x)	xx (xx.x)
System Organ Class 2	xx (xx.x)	xx (xx.x)	xx (xx.x)
Preferred Term 1	xx (xx.x)	xx (xx.x)	xx (xx.x)
Preferred Term 2	xx (xx.x)	xx (xx.x)	xx (xx.x)

Note(s): Adverse event terms were coded using MedDRA dictionary version 18.1. Subjects are counted once within each level of summary.

Source: Listing xx.x.x.x, Program: xxxxx.sas, Output: T xx.x x x xxxx.rtf, Generated on: DDMMMYYYY HH:MM

Programmer Note: Order SOC by decreasing frequency and preferred term by decreasing frequency within SOC based on overall incidence.

Protocol Number: NI-AC303

Drug Class	SB204
Preferred Name	(N=XXX)
Subjects Who Took at Least One Concomitant Medication	xx (xx.x)
Drug Class 1	xx (xx.x)
Preferred Name 1	xx (xx.x)
Preferred Name 2	xx (xx.x)
Preferred Name 3	xx (xx.x)
etc.	xx (xx.x)
Drug Class 2	xx (xx.x)
Preferred Name 1	xx (xx.x)
Preferred Name 2	xx (xx.x)
Preferred Name 3	xx (xx.x)
etc.	xx (xx.x)
Drug Class 3	xx (xx.x)
Preferred Name 1	xx (xx.x)
Preferred Name 2	xx (xx.x)
	xx (xx.x)

Note(s): Subjects are counted only once at each level of summarization.

Concomitant medications are all medications taken during the study period, including those started before but ongoing at first dose. All medications were coded using WHO Drug dictionary version March 2016.

Source: Listing xx.x.x.x, Program: xxxxx.sas, Output: T xx.x x x xxxx.rtf, Generated on: DDMMMYYYY HH:MM

Programmer's Note(s): Continue with all drug classes and preferred names which appear in the data. Sort drug classes and within drug classes, preferred terms by decreasing overall frequency.

Protocol Number: NI-AC303

Table 14.2.1.

Summary of Duration and Extent of Drug Exposure
Safety Population

	SB204 Experienced	SB204 Naïve	Overall
	(N=XXX)	(N=XXX)	(N=XXX)
Overall Duration of Exposure (Days)			
Number of Subjects with Exposure	xx	XX	XX
Mean (SD)	xx.x (xx.xx)	xx.x (xx.xx)	xx.x (xx.xx)
Median	XX.X	XX.X	XX.X
Min, Max	X.X, XX.X	X.X, XX.X	x.x, xx.x
Unknown	,	,	•
Days of Exposure			
n	xx	xx	XX
Mean (SD)	xx.x (xx.xx)	xx.x (xx.xx)	xx.x (xx.xx)
Median	XX.X	XX.X	XX.X
Min, Max	x.x, xx.x	x.x, xx.x	X.X, XX.X
Unknown			
Areas of Application			
Face	xx (xx.x)	xx (xx.x)	xx (xx.x)
Upper Back	xx (xx.x)	xx (xx.x)	xx (xx.x)
Upper Chest	xx (xx.x)	xx (xx.x)	xx (xx.x)
Shoulders	xx (xx.x)	xx (xx.x)	xx (xx.x)
Other	xx (xx.x)	xx (xx.x)	xx (xx.x)
Extent of Exposure (grams)			
Mean (SD)	xx.x (xx.xx)	xx.x (xx.xx)	xx.x (xx.xx)
Median	XX.X	XX.X	XX.X
Min, Max	x.x, xx.x	x.x, xx.x	x.x, xx.x
Unknown	xx (xx.x)	xx (xx.x)	xx (xx.x)
1-100 grams	xx (xx.x)	xx (xx.x)	xx (xx.x)
>100-330 grams	xx (xx.x)	xx (xx.x)	xx (xx.x)
>330-675 grams	xx (xx.x)	xx (xx.x)	xx (xx.x)
>675 grams	xx (xx.x)	xx (xx.x)	xx (xx.x)

Notes: All exposure endpoints includes exposure to SB204 from the previous study (NI-AC301 or NI-AC302), if applicable. Duration of Exposure = Date of Last Drug Administration - Date of First Drug Administration + 1 day. Days of exposure will be defined as the total number of days that the subject reported taking study medication. Areas of application indicate if the subject ever applied drug to that area. Each subject is counted only once per area.

Extent of exposure is determined as: 0.9 grams times the number of application areas times the number of days applied. Application to neck and jawline are considered part of application to the face when determining extent of exposure. Source: Listing xx.x.x.x.x, Program: xxxxx.sas, Output: T xx.x x x xxxx.rtf, Generated on: DDMMMYYYY HH:MM

Protocol Number: NI-AC303

Table 14.2.2.1
Inflammatory Lesion Counts by Study Visit (Face Only)
Safety Population

		SB204 (N=XXX)		
		Count	Absolute Change	Percent Change
Visit	Statistic		from Baseline	from Baseline
Baseline	N	XX		
	Mean	XX.X		
	SD	XX,XX		
	Median	XX		
	Min. to Max.	XX to XX		
Week 4	N	XX	XX	XX
	Mean	XX.X	XX.X	XX.X
	SD	XX, XX	XX,XX	XX,XX
	Median	XX	XX,X	XX,X
	Min. to Max.	XX to XX	XX to XX	XX to XX
Week 12	N	XX	XX	XX
	Mean	XX.X	XX.X	XX.X
	SD	XX,XX	XX,XX	XX,XX
	Median	XX	XX,X	XX,X
	Min. to Max.	XX to XX	XX to XX	XX to XX

Source: Listing xx.x.x.x, Program: xxxxx.sas, Output: T xx.x x x xxxx.rtf, Generated on: DDMMMYYYY HH:MM

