3.1.3 EXTENT OF EXPOSURE

Extent of exposure will be calculated based on total number of days of study drug application and the body surface area treated (face, upper back, upper chest/shoulders).

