3.4 DOSAGE/DOSE REGIMEN

SB204 will be dispensed from a dual-chamber pump designed to deliver approximately equal amounts of NVN1000 Gel and hydrogel. NVN1000 Gel will be opaque and the hydrogel will be clear. The subject will instantly mix the two substances in the palm of the hand and then immediately massage a thin layer over the acne affected areas once daily after washing. The product should be mixed for about 5 seconds until thoroughly combined with a uniform opaque appearance then applied with the fingertips. Subjects should apply SB204 prior to bedtime.

Up to 2.7 g of SB204 4% will be applied evenly over the acne affected area, including the face, chest, back, and upper shoulders once a day for a period of up to 40 weeks (280 days). The amount of SB204 per application will vary depending on the areas to be treated as shown in Table 1 below. One pump stroke (0.9 g) will be used for the face. Application to the face, upper back and upper chest/shoulders will require up to 2.7 g (three (3) pump strokes).

Table 1: Dosing Amount by Area

Area (BSA)	Number of Pump Strokes	Amount of Product	
Face (3%)	1	0.9 g	
Upper Back (6%)	1	0.9 g	
Upper Chest/Shoulders (8%)	1	0.9 g	

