7.7 EXTENT OF EXPOSURE

Extent of exposure will be based on days of treatment and the body surface area treated (face, upper back, and/or upper chest/shoulders) as collected at each visit for each subject. AEs will also be summarized by extent of exposure to determine if there is a safety signal due to duration of exposure or total body area exposed.

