### 4.4 Extent and Duration of Exposure

Summaries of the duration of exposure, days of exposure, and extent of exposure (calculated total grams) to study drug will be presented, overall and by whether previously randomized to SB204 (SB204 experienced) or randomized to Vehicle (SB204 naïve). This information plus study drug management details will be listed as well. All exposure endpoints will take into account whether the subject received SB204 in the previous study (NI-AC301 or NI-AC302).

Duration of exposure will be defined as:

Date of Last Drug Administration – Date of First Drug Administration + 1 day

Where date of first drug administration is the date of first treatment in the previous pivotal study for subjects randomized to SB204 in the previous study, and date of first dose in the LTS for subjects randomized to vehicle in the previous study.

Days of exposure will be defined as the total number of days that the subject reported taking study medication, and includes the days of exposure to SB204 in the previous study (NI-AC301 or NI-AC302) if applicable.

Extent of exposure will be based on the number of areas treated (face, upper back, and/or upper chest/shoulders, and any other areas reported) and the number of days with treatment. For subjects randomized to SB204 in the previous studies, drug was only applied to the face so for the days of exposure from the previous studies, it will be assumed that there is only one area of application, i.e. the face.

Each application is equal to 0.9 g. Extent of exposure is estimated as the sum of application areas (face only=1, face and chest=2, etc.) times the number of days of application to those areas times 0.9g. For example, a subject who applies 200 applications to the face only will have extent of exposure = 180g, while a subject who applies 100 applications to the face and 50 applications to the upper back will have extent of exposure = 135 g. The maximum extent of exposure would be: [0.9 grams x number of days on treatment in previous study] + [0.9 grams x 4 areas x number of LTS days on treatment]. Most subjects will have less exposure than this, so extent of exposure will be categorized logically depending on actual distribution of subjects. Initially, quartiles will considered.

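### The SAP measures extent of exposure only in grams, so the protocol's question about adverse events and body area treated has no planned analysis

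*SAP*

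**What the plan says.** **Protocol.** Section 3.1.3 states: "Extent of exposure will be calculated based on total number of days of study drug application and the body surface area treated". Section 7.7 repeats the basis ("Extent of exposure will be based on days of treatment and the body surface area treated") and gives the reason for summarizing AEs by extent: "to determine if there is a safety signal due to duration of exposure or total body area exposed". Table 1 in section 3.4 gives the areas as face 3%, upper back 6% and upper chest/shoulders 8% as one combined area. Each takes one pump stroke of 0.9 g. The three sum to the 17% BSA on which the risk statement in section 1.5 rests.

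**SAP.** Section 4.4 estimates extent as the sum of application areas "times the number of days of application to those areas times 0.9g", and the notes to mock Table 14.2.1 give the same rule: "Extent of exposure is determined as: 0.9 grams times the number of application areas times the number of days applied". Section 4.4 offers two worked examples: "a subject who applies 200 applications to the face only will have extent of exposure = 180g", and "100 applications to the face and 50 applications to the upper back will have extent of exposure = 135 g". SAP Table 1 still mentions BSA in its column header but gives no percentages, and it lists upper chest and shoulders as two areas of 0.9 g each. Section 4.5.1 links the search for a signal to duration windows and otherwise summarizes AE incidence by gram category. Treated areas appear only as ever-treated counts in Table 14.2.1 and as visit-level ticks in Listing 16.2.6.

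**The concern.** The protocol names two dimensions along which a safety signal might appear: how long the drug is applied, and how much skin it is applied to. The SAP carries the first forward. For the second it substitutes grams, which count areas without regard to their size. No SAP section, table or listing computes BSA, and no AE table is arranged by body area. The SAP does not say that it has changed the protocol's measure.

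Safety is the primary objective. If AEs rise with treated skin area, the planned gram bands would mix subjects who treat small and large areas, and would mix area with duration. The body-area question in section 7.7 would then go unanswered, although the data to answer it are collected at every visit.

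**Working it through.** **Inputs.** BSA percentages and 0.9 g per area from Protocol Table 1; the gram rule and worked examples from SAP 4.4; the gram bands (1-100, >100-330, >330-675, >675 g) from mock Table 14.2.1; 280 days as the full treatment period.

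**Formulas.** Grams = 0.9 × sum over areas of days applied. BSA-%-days = sum over areas of (BSA % × days applied).

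**1. The SAP's own examples.**
- 0.9 × 200 = 180 g, and 0.9 × (100 + 50) = 135 g. Both reproduce exactly.
- In BSA-%-days: 200 × 3 = 600, and 100 × 3 + 50 × 6 = 600. The two subjects differ by 45 g, yet have the same area-weighted exposure.

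**2. One area for 280 days.**

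| Area treated | Grams | BSA-%-days |
|---|---|---|
| Face (3%) | 0.9 × 280 = 252 | 3 × 280 = 840 |
| Upper back (6%) | 252 | 6 × 280 = 1,680 |
| Upper chest/shoulders (8%), one stroke as in the protocol | 252 | 8 × 280 = 2,240 |
| Upper chest and shoulders, two areas as in the SAP | 1.8 × 280 = 504 | 2,240 |

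Face against upper back is 1,680 / 840 = 2-fold at equal grams, under both documents. The wider range, 2,240 / 840 = 2.7-fold, holds only on the protocol's one-stroke mapping.

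**3. Grams per 1% BSA.** Face 0.9 / 3 = 0.30; upper back 0.9 / 6 = 0.15; upper chest/shoulders 0.9 / 8 = 0.1125 at one stroke, or 1.8 / 8 = 0.225 if counted as two areas. Grams are therefore not proportional to area. Dividing grams by days of application does not recover it: any single area gives 0.9 g a day.

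**4. Can the bands reverse the order?** Yes. Upper back only for 110 days is 99 g (band 1-100) and 660 BSA-%-days. Face only for 120 days is 108 g (band >100-330) and 360 BSA-%-days.

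**5. How often?** An illustrative grid took every combination of the protocol's three areas at 10 to 280 days in steps of 10, and compared all pairs falling in different bands.
- One stroke for upper chest/shoulders: 261 of 12,078 pairs were reversed (2.2%).
- Two strokes for that region: 107 of 13,155 (0.8%).
- No reversal occurred at equal days. On the protocol's mapping the smallest pair of areas (3% + 6% = 9%) exceeds the largest single area (8%).

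The grid shows what is possible and does not forecast the trial's distribution. With the SAP's four areas, a reversal at equal days would need an uneven split of the 8%. For example, upper back alone (6%) exceeds face plus upper chest only if the upper chest is under 3%. The documents give no split.

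**The case against.** The strongest reply has four parts.

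- **Equal grams per area is the protocol's own dosing figure.** This stands. A reader might infer that the gram formula is wrong. It is not: it is a valid estimate of product applied and should stay.
- **The protocol never defines BSA-days.** This also stands. The synopsis describes BSA as judged from locations, and sections 3.1.3 and 7.7 illustrate it by naming locations. A count of locations times days is an arguable, coarse reading, and Protocol 7.1 leaves detail to the SAP. BSA-days is therefore one way to express the protocol's wording and not a named endpoint that was omitted. But the quantity named is surface area, Table 1 gives each location's percentage, and section 7.7 asks about total body area. A bare count cannot answer that question.
- **Area data are not lost.** True. Areas, days and grams appear by visit in Listing 16.2.6, so a reader could approximate BSA-days. Nothing in the SAP plans to do so, and no AE summary uses area.
- **The study is open-label and descriptive, and the cut points may change.** SAP 4.4 does allow bands to follow the observed distribution. New cut points on grams would still not restore area.

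**Conclusion.** The gap is real. The protocol asks whether AEs relate to the body area treated, and the SAP plans neither a BSA measure nor an AE summary by area. At equal grams, treated area can differ 2-fold (face against upper back) under either document's mapping. The 2.7-fold figure depends on treating upper chest/shoulders as one 0.9 g area.

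A reader might go further and infer that the gram bands generally invert the order of skin exposure. The documents do not support this. Reversals are possible but uncommon on the grid and, with the protocol's three areas, need unequal numbers of days. The more likely effect is a blurred gradient.

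The conclusion rests on using the Protocol Table 1 percentages as area weights. The size of any effect on AE results cannot be stated, because the documents give no distribution of treated areas.

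**What to change.** 1. **Keep grams** as the dose measure.
2. **SAP 4.4 and Table 14.2.1:** for NI-AC303 days, add BSA-days (the sum over visit intervals of the Protocol Table 1 % for the areas ticked × days of exposure in the interval) and mean treated BSA (BSA-days / days of exposure). Show both by SB204 Experienced, SB204 Naïve and Overall.
3. **SAP 4.5.1:** add one table of treatment-emergent AEs by category of mean treated BSA beside the gram-band table. Mean treated BSA separates area from duration, which BSA-days alone would not. Fix the cut points before database lock. Constant patterns on the protocol's areas can only give 3, 6, 8, 9, 11, 14 or 17%.
4. **Mapping rules:** count 8% if upper chest or shoulders is ticked, with a sensitivity version at 4% each (an assumption, as no split is given). Treat jaw and neck as face, as the SAP already does for grams. Report how many subjects used other sites with no stated BSA.
5. **Reconcile the documents:** the protocol has one combined upper chest/shoulders area and a 2.7 g daily maximum, while the SAP has two separate areas and a maximum built on four.

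**Cost:** SAP and shell wording, a short derivation from data already collected, one more exposure measure and one more AE table. The derivation assumes that every area ticked at a visit was treated on all days of exposure in that interval, and it needs the assumption about the 8% split.
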